6.3. Handling of Missing Data

Subjects who withdraw from the study after the initiation of the study drug will not be replaced and available data for these subjects until the point of withdrawal will be summarized.

Any missing baseline assessments (last assessment prior to initial study drug treatment) will not be imputed.

For categorical variables with missing values, a category documenting the frequency of missing values will be displayed in the summary tables.

25-April-2022

Subjects who withdraw early from study will be encouraged to have all EOS procedures and assessments completed at an early termination visit.

For ASES function subscale, if the responses to 1 or 2 items are missing, the ASES function subscale score will be calculated as = $10 \times$ (mean of the scores for the non-missing activity items) \times 5/3. If more than 2 items of the responses to the ASES function subscale are missing, then the ASES function subscale score will be considered as missing. If either of the pain subscale or function subscale score is missing, then the ASES composite score will be considered as missing.

There will be no imputation of missing values for safety data, however missing relationship between AE and study drug will be considered as related to study drug following worst case principle. Missing severity of an AE will be summarized as a severe AE. Duration of an AE will be classified in the "> 21 Days" category if an AE is ongoing for more than 21 days by the time of the last visit of the subject in the study.

Immunogenicity samples with a positive titer value will undergo a log transformation for analyses. Samples with titer level less than 10 will be assigned or imputed as a log transformed titer of 1 for analyses.

6.3.1. Handling of Missing Data for Sensitivity Analysis of Primary Endpoint

The primary endpoint is the change from baseline in the adapted ASES composite score for the affected shoulder at Day 95. This value could be missing if the subject has missing data due to discontinuation from the study prior to Day 95, due to a missed assessment, lost to follow-up, or other.

A sensitivity analysis using a mixed model with repeat measurements (MMRM) with imputation using a tipping point analysis (refer to section 7.9.4.1) will be performed on the primary endpoint to assess the impact of missing values. If the primary analysis result is not significant (p-value greater than 0.05), no sensitivity analysis (tipping point) will be completed.

6.3.2. Imputation of Partial Dates

6.3.2.1. TEAE Status for Completely Unknown Start Date

The following rules will apply in cases where start date of an AE is completely unknown:

- If the AE onset date is unknown and the end date is after first injection on Day 1 or ongoing, then the AE will be considered a TEAE.
- If the AE onset date is unknown and the end date is before first injection on Day 1, then the AE will not be considered a TEAE.
- If both the start and end dates are unknown (or end date is ongoing), then the AE will be considered a TEAE, following the worst-case principle.

If the AE onset date is partly present and month/year is prior to the first injection on Day 1, then the AE will not be considered a TEAE.

6.3.2.2. Concomitant Status of Medication/Non-drug Therapy for Completely Unknown Start Date

The following rules will apply in cases where start date of medication is completely unknown:

- If the medication onset date is unknown and the end date is after the date of screening but before the Day 95/ET Visit or medication is ongoing, then the medication will be considered as concomitant.
- If the medication onset date is unknown and the end date is before the date of screening, then the medication will not be considered as concomitant.
- If both the start and end dates are unknown, then the medication will be considered as concomitant. This approach is considered to be the most conservative following the worst-case principle.

If the medication onset date or end date is partly present and month/year is prior to the date of screening, then the medication will not be considered as concomitant. If the medication onset date or end date is partly present and month/year is after to the date of screening or medication is ongoing, then the medication will be considered as concomitant.

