3.2. Eligibility Criteria for Subject Selection

3.2.1. Inclusion Criteria

In order to be eligible to participate in the study, prior to randomization subjects must:

- 1. Be \geq 18 years of age at the time of consent and can be male or female.
- 2. Agree not to use pain medications for the duration of the study period and for 2 weeks prior to the Screening Visit. Pain medications include but are not limited to: methadone, buprenorphine, opioids (eg, codeine, heroin, hydrocodone, hydromorphone, morphine, oxycodone), and cannabis.

Note: Nonsteroidal anti-inflammatory drugs (NSAIDs) (ibuprofen, etc) and Tylenol (acetaminophen) are allowed.

- 3. Have idiopathic unilateral AC defined as subjects with passive external rotation that demonstrates at least a 30% loss of ROM tested at 0°, 45°, and 90° abduction in the affected shoulder compared to the contralateral shoulder in the supine position. In the event that 45° and 90° cannot be achieved due to pain or restriction, the amount of external rotation available at maximum attainable abduction ROM is permissible as the second and third measurements.
- 4. Have an adapted ASES function subscale score of < 35 in the affected shoulder at the Screening and Day 1 Visits.
- 5. Have unaffected ROM in the contralateral shoulder as determined by the investigator.
- 6. Be able (in a supine position) to have the affected arm passively rotated to at least a neutral position within their level of pain tolerance with the elbow at the side (against the body) and flexed to 90°.
- 7. Be willing to undergo x-ray of the affected shoulder and MRI of the affected and contralateral shoulder as required by the protocol.
- 8. Agree to participate in supervised, in-office PT sessions and to complete home exercises at designated time points during the study.
- 9. Agree to avoid general lifting and carrying of no more than 10 pounds, and lifting of no more than 5 pounds overhead for 21 days after each treatment, except during supervised PT sessions.
- 10. Be able to read, understand, and independently complete patient reported outcome instruments in English.

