4.4. Prior and Concomitant Medications

All medications will be coded using World Health Organization (WHO) Drug Dictionary, by active ingredient and WHO anatomical therapeutic chemical (ATC) classification of ingredients. The dictionary version to be used will be defined in the Data Management Plan (DMP).

A prior medication (or non-drug therapy) is defined as any medication (or non-drug therapy) taken prior to the Screening Visit and stopped before the Screening Visit.

A concomitant medication (or non-drug therapy) is any medication (or non-drug therapy) taken on or after the Screening Visit through the Day 95/ET Visit or taken prior to the Screening Visit and continuing during the study.

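### SAP 6.3.2.2 lets a partial onset date before screening override an end date that shows on-study use, contrary to the SAP's own definition of concomitant medication

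*SAP*

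**What the plan says.** SAP 4.4 defines the two categories by actual use. A prior medication or non-drug therapy is one "taken prior to the Screening Visit and stopped before the Screening Visit". A concomitant one is "taken on or after the Screening Visit through the Day 95/ET Visit or taken prior to the Screening Visit and continuing during the study".

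SAP 6.3.2.2 then gives rules for incomplete dates. Its bullets deal with a completely unknown onset, and there the end date decides: if the "onset date is unknown and the end date is after the date of screening but before the Day 95/ET Visit or medication is ongoing", the item is concomitant, and if it ended before screening it is not. If both dates are unknown it is concomitant, with the comment "This approach is considered to be the most conservative following the worst-case principle".

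A closing paragraph of two sentences covers partial dates. Sentence 1 withholds concomitant status: "onset date or end date is partly present and month/year is prior to the date of screening, then the medication will not be considered". Sentence 2 grants it, on this condition for either date: "partly present and month/year is after to the date of screening or medication is ongoing, then the medication will be considered as concomitant".

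SAP 7.6 uses the classification for frequency tables by treatment group in the Safety Population and for listings. Both categories are tabulated and listed.

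**The concern.** Whether use continued into the study depends on when it stopped, not on when it started. A rule that lets a partial onset date before screening settle the matter alone will mislabel anything that began earlier and stopped on study. Under SAP 4.4 such a record is concomitant. It cannot be prior either, because it did not stop before screening, so read literally it belongs to neither category.

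What is at stake is the accuracy and reproducibility of the concomitant-medication table. That table has some interest here because simple analgesics are permitted (SAP 3.2.1, criterion 2: NSAIDs "and Tylenol (acetaminophen) are allowed") and the pain item makes up half of the adapted ASES composite (SAP 4.7.1.3). The table is where a reader would look for a by-arm summary of that use. Where the two sentences conflict, two programmers following the same text could also produce different tables.

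**Working it through.** There is no stated figure to reproduce; the check is a comparison of rules. The inputs are the two sentences of the partial-date paragraph and the bullets in SAP 6.3.2.2, and the definitions in SAP 4.4.

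**Partial onset, month/year before screening**

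| End date | Sentence 1 | Sentence 2 | Result of 6.3.2.2 | SAP 4.4 |
|---|---|---|---|---|
| Complete, before screening | applies | no | not concomitant | prior (agrees) |
| Partial, before screening | applies | no | not concomitant | prior (agrees) |
| Complete, after screening | applies | no | not concomitant | concomitant (**contradiction**) |
| Partial, after screening | applies | applies | two opposite answers | concomitant |
| Ongoing | applies | applies | two opposite answers | concomitant |
| Unknown | applies | no | not concomitant | cannot be determined |

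*Row 3.* As an illustration, take onset in January with the day unknown, screening in March and a stop date of 10 April. The onset is partial and precedes screening, so sentence 1 applies. Neither date is partial and after screening, and the item is not ongoing, so sentence 2 does not apply. The result is not concomitant. If the onset had been wholly unknown with the same stop date, the first bullet would make it concomitant. Knowing more about the start date moves the record out of the table.

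*Rows 4 and 5.* Both sentences apply and disagree. The section gives no order of precedence.

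*Row 6.* SAP 4.4 cannot settle this one. The bullets make an item with both dates unknown concomitant, on a worst-case argument. Here the onset month is known to precede screening and the end is just as unknown, yet the answer is the less conservative one.

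**Partial onset in the screening month**

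The onset month is neither before nor after screening, so the outcome rests on the end date:

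- Complete end date, before or after screening: neither sentence applies.
- End date unknown: neither sentence applies.
- Partial end date before screening: not concomitant, which agrees with SAP 4.4.
- Partial end date after screening, or ongoing: concomitant, which agrees with SAP 4.4.

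**Partial onset after screening**

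Every combination gives concomitant, in line with SAP 4.4.

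The defect therefore comes from the words *onset date or* in sentence 1, together with the lack of any statement that a known end date takes precedence.

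**The case against.** The strongest reply is that the definition governs and the date rules only fill gaps. SAP 6.3.2 is about imputing partial dates, and the heading of 6.3.2.2 speaks of a completely unknown start. A complete stop date after screening already settles status under SAP 4.4, so nothing needs imputing. The bullets use the end date in just this way, which suggests the intent. That is a sensible reading, and a careful programmer might adopt it. But the SAP nowhere states that precedence, and the paragraph expressly addresses partial onset dates. The argument limits how far the error would spread in practice; it does not remove it from the text.

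A second reply concerns consequence, and most of it stands:

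- The status feeds only descriptive Safety Population tables and listings (SAP 7.6).
- The primary model contains treatment, visit and their interaction (SAP 7.9.1.1). Neither it nor any secondary model uses medication status.
- A subject is counted once per medication, so another on-study record of the same drug would still place that subject in the concomitant table.
- AC treatment after Day 1 is reported separately as a protocol deviation (SAP 4.4.1), and prohibited medication is a listed deviation type (SAP 4.2).

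A reader might infer that every medication with a partial early onset is dropped, so that chronic use is systematically undercounted. The documents do not support that. Sentence 2 expressly keeps ongoing items, and those with a partial end date after screening, as concomitant. For them the text conflicts with itself; it does not plainly exclude them.

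**Conclusion.** The point holds in a narrow form and is minor. Read literally, sentence 1 gives a result that contradicts SAP 4.4 in one combination: partial onset before screening with a complete end date after it. In a second, partial onset before screening with an unknown end date, it departs from the section's own worst-case handling. In two more, ongoing use and a partial end date after screening, the text answers both ways. A partial onset in the screening month with a complete or unknown end date has no rule.

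The number of affected records cannot be determined, because the documents give no frequency of partial dates. Recording all prior AC treatments in addition to the 90-day look-back (SAP 3.9) makes imprecise start dates plausible, but that is an assumption about the data.

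A reader might also infer that the rule could hide an analgesic imbalance and so undermine the primary result. The documents do not support that either. The table counts any use by active ingredient, without dose or timing relative to the pain item. Analgesics first taken after screening and recorded with an on-study onset do not meet the onset condition of sentence 1.

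The conclusion assumes that the paragraph is programmed as written, without an unstated rule that SAP 4.4 takes precedence.

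**What to change.** Rewrite the partial-date paragraph of SAP 6.3.2.2 so that the end date or ongoing status decides first:

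- Not concomitant only if the end date precedes screening, whether it is complete or is partial with a month/year before screening.
- Otherwise concomitant. This includes ongoing use, an unknown end date, and a partial end date whose month equals the screening month.

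In practice, delete *onset date or* from sentence 1. Deleting those words alone leaves sentence 2 still keyed partly to onset, so align it too: a partial onset date, including one in the screening month, should never override a known end date.

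The cost is a two-sentence paragraph and the matching lines of the derivation. No new data are needed and no efficacy analysis changes.

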6.3.2.3. Missing Last Menstrual Date

Missing date of last menstrual period will be imputed with the last day of the month and missing onset month will be imputed with December.

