8.2.2. Medical and Surgical History

Medical and surgical history will be obtained at the Screening Visit. Medical history will include a review of the following systems: general, dermatological, respiratory, cardiovascular, gastrointestinal, genitourinary, gynecological, endocrine, musculoskeletal, hematological, neuropsychological, immune (allergies), and head, eyes, ears, nose, and throat. Historical and current medical conditions, including date of last menstrual period for female subjects, will be recorded.

In addition, any history or current collagen mediated disorders (including but not limited to Garrod's pads, Dupuytren's nodules, plantar nodules, PD, AC of other joints, etc) will be recorded (excluding the current AC episode).

History of tobacco and alcohol use (never, current, former) will also be collected.

Surgical history will include a review of all surgical procedures completed in the prior 5 years and any surgery completed at any time in the affected shoulder.

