3. STUDY DESIGN AND MEASURES

3.1. Study Design

This is a Phase 2b, double-blind, placebo-controlled study of the safety and efficacy of EN3835 for the treatment of AC of the shoulder.

This study will randomize approximately 180 subjects to receive EN3835 or placebo so that approximately 142 evaluable subjects will complete the study. To be eligible for treatment, a subject must have unilateral idiopathic AC of the shoulder with restricted ROM and function in the affected shoulder.

Subjects will be screened for study eligibility within 28 days before the first injection of study treatment. During screening subjects will undergo MRIs of both shoulders. The affected shoulder MRI will be reviewed through a central blinded read to determine subject eligibility (that each subject has AC without clinically significant confounding pathologies).

Subjects who were in screening (those who had completed or were in the process of screening) for the study at the time of any COVID-19 interruption but who had not been dosed with EN3835 may be rescreened. If a subject rescreens within 30 days of their original screening MRI date and AC was confirmed in the affected shoulder by the MRI central review committee, and the unaffected shoulder MRI was unremarkable, the subject will not need to have a repeat MRI of either shoulder. Other AC shoulder screening assessments will be determined on a case-by-

case basis as to whether or not the subject will need to repeat. All repeat screening assessments must be completed within the screening window.

Following screening, eligible subjects will be randomized 1:1 to receive EN3835 0.58 mg/1 mL or volume matched placebo.

EN3835 or placebo will be administered by ultrasound-guided injection at the injection site

following the administration of a local anesthetic. Subjects will receive up to 3 injections of study treatment (total dose: 1.74 mg) separated by at least 21 days (on Day 1, Day 22, and Day 43). Following each injection, subjects will remain under observation for at least 30 minutes. All subjects will undergo standardized, supervised, in-office physical therapy (PT) sessions starting 7 days after each treatment session and will complete 2 sessions per week for 2 weeks with a minimum of 2 days between each PT session. In addition, subjects will complete standard home exercises starting 3 days after each injection of study treatment through the Day 95 Visit.

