- 11. If female, be of nonchildbearing potential (history of hysterectomy, bilateral oophorectomy, bilateral tubal ligation, or postmenopausal with no history of menstrual flow in the 12 months prior to the Screening Visit); or, if of childbearing potential, be nonpregnant, nonlactating and agree to use effective contraception when with a male partner for the duration of the study (and for 28 days after any active treatment period for subjects who early terminate). Acceptable forms of contraception include hormonal measures (oral contraceptive pills, contraceptive patch, contraceptive ring, and

injections), intrauterine devices, double barrier method (condom plus diaphragm, condom or diaphragm plus spermicidal gel or foam), surgical sterilization of the male partner, and abstinence.

- 12. If male with reproductive potential, agree to use effective contraception (abstinence, surgical sterilization [vasectomy], or condom with spermicide) with a female partner of child-bearing potential for the duration of the study (and for 28 days after any active treatment period for subjects who early terminate).
- 13. Be willing and able to comply with all protocol required visits and assessments.
- 14. Be adequately informed and understand the nature and risks of the study and be able to provide consent as outlined in Protocol Section 10.1.3.

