3.6. Medical and Surgical History

A medical and surgical history of the subject will be taken during the Screening Visit. Medical history will include relevant diagnoses and procedures/therapies with onset/resolutions dates.

Medical history will include a review of the following systems: general, dermatological, respiratory, cardiovascular, gastrointestinal, genitourinary, gynecological, endocrine, musculoskeletal, hematological, neuropsychological, immune (allergies), and head, eyes, ears, nose, and throat. Historical and current medical conditions, including date of last menstrual period for female subjects, with onset/resolutions dates will be recorded.

In addition, any history or current collagen mediated disorders (including but not limited to Garrod's pads, Dupuytren's nodules, plantar nodules, Peyronie's disease, AC of other joints, etc) will be recorded (the current AC episode will not be recorded on the medical history case report form [CRF] - see next section).

Surgical history will include a review of all surgical procedures completed in the prior 5 years and any surgery completed at any time in the affected shoulder.

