4.3. Demographic and Baseline Characteristics

Demographics and baseline characteristics include the following parameters:

- Age.
- Height (at Screening).

- Weight (at Screening).
- Body Mass Index (BMI) in kg/m² (at Screening) (refer to Table 16).
- Gender.
- Race.
- Ethnicity.
- Time since last menstrual period for female subjects.
- Report of tobacco and alcohol use
 - Alcohol use (Never, Current, and Former).
 - Tobacco use (Never, Current, and Former).

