7.3. Demographics and Baseline Characteristics

Demographics and baseline characteristics will be summarized by treatment group and overall, for the safety, mITT, and PP populations.

Age, height (at baseline), body weight (at baseline), BMI in kg/m^2 , and time since last menstrual period for female subjects will be summarized as continuous variables using descriptive statistics.

Age group, gender, race, and ethnicity will be summarized as categorical variables using frequency counts and percentages.

History of tobacco and alcohol use will be summarized using frequency counts and percentages as:

- Alcohol use (Never, Current or Former).
- Tobacco use (Never, Current or Former).

All demographic and baseline characteristics will be presented in by subject listings.

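### The rule for partial last-menstrual-period dates has no cap at Screening, so baseline time since last menstrual period can take impossible negative values

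*SAP*

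**What the plan says.** The rule is a single sentence in SAP section 6.3.2.3: a missing date is "imputed with the last day of the month and missing onset month will be imputed with December". It sets no upper bound, and no other section of the protocol or SAP supplies one.

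The date is collected as part of the medical history. Protocol section 8.2.2 states: "Medical and surgical history will be obtained at the Screening Visit". SAP section 3.6 lists the item among the history data, "including date of last menstrual period for female subjects, with onset/resolutions dates will be recorded".

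The derived quantity is a listed baseline characteristic in SAP section 4.3: "Time since last menstrual period for female subjects". Under SAP section 7.3, "time since last menstrual period for female subjects will be summarized as continuous variables using descriptive statistics", by treatment group and overall, for the safety, mITT and PP populations. Table 16 in SAP section 6.2, which defines the derived variables, gives neither a formula nor a reference date for it.

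**The concern.** A date obtained at Screening has a natural upper limit, namely Screening itself. A rule that moves an incomplete date to the last day of its month, or to December, ignores that limit. If the known part of the date is the Screening month or year, the rule moves the event into the future and the elapsed time becomes negative. This is a stated rule that returns a wrong value, not merely an omitted detail.

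What is at stake is small. The mean, SD, median and minimum of one baseline line could be wrong in up to three population tables. A negative time since last menstrual period in a published table is a visible error.

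**Working it through.** The documents state no figure on this point, so there is none to reproduce. The check applies the rule to calendar dates.

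**Inputs.** The rule is from SAP 6.3.2.3. Collection at Screening is from Protocol 8.2.2 and SAP 3.6. Screening dates are assumed to be spread evenly over 1 July 2020 to 28 February 2022, inferred from the estimated study period of July 2020 to June 2022 in the protocol synopsis. That window has 608 days: 12 months of 31 days, 6 of 30 and 2 of 28.

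**Formula.** Time since last menstrual period = Screening date − imputed date. It is negative when the imputed date is later than Screening.

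**Example, Screening on 10 March 2021.**
- Known only as March 2021: imputed 31 March 2021; 10 − 31 = −21 days.
- Known only as 2021: imputed 31 December 2021. 10 March is day 69 of the year; 69 − 365 = −296 days.
- True date 20 February 2021 with the day missing: imputed 28 February; +10 days, a possible value.
- True date 1 June 2015: +2080 days with the day missing and +1896 with the month missing, both possible.

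**When the known part matches Screening.** The imputed date is later than Screening unless Screening falls on the last day of the month (day missing) or on 31 December (month missing). The window has 20 month-ends and two 31 Decembers:
- Day missing: (608 − 20)/608 = 96.7%.
- Month missing: (608 − 2)/608 = 99.7%.

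**Without that condition.** Take a true date spread evenly over 0 to 28 days before Screening (an assumption for a currently menstruating woman). There are 608 × 29 = 17,632 combinations of Screening date and true date.
- Day missing: the combinations giving a date after Screening number 464 in a 31-day month, 435 in a 30-day month and 378 in a 28-day month. (12 × 464 + 6 × 435 + 2 × 378)/17,632 = 8,934/17,632 = 51%.
- Month missing: the combinations not giving a date after Screening are 2 × 29 = 58 with Screening on 31 December and 2 × 406 = 812 with Screening in January and the true date in the previous year. 1 − 870/17,632 = 95%.

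The same enumeration over other intervals gives:

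| True date before Screening | Day missing | Month missing |
|---|---|---|
| 0–28 days | 51% | 95% |
| 0–35 days | 41% | 94% |
| 0–90 days | 16% | 86% |
| 0–364 days | 4% | 53% |
| More than 12 months | 0% | 0% |

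**Postmenopausal women.** The inclusion criterion defines them as "postmenopausal with no history of menstrual flow in the 12 months prior to the Screening Visit". Their last period therefore lies in an earlier calendar year than Screening, and even 31 December of that year precedes Screening. If half of the women with partial dates were postmenopausal and the rest followed the 0–28 day row, the shares would be 25% and 48%; at 90% they would be 5% and 10%. These mixes are assumptions.

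**After the fix.** With the imputed date capped at Screening, the share after Screening is 0% in every row and the minimum elapsed time is 0 days.

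**The case against.** A reader might infer that the rule usually gives a date after Screening, and that the reported table does contain negative values. The documents support neither. The 96.7% and 99.7% above apply only when the known month or year is that of Screening. Across partial dates generally, the share runs from 0% to 95%, depending on menopausal status, the timing of the last period and which part of the date is missing. The documents do not say how many dates are partial; there may be none. What they support is that negative values can occur.

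Two further objections have some force. First, Table 16 names no reference date, so Screening is an inference for the elapsed time. SAP 3.1 says "Subjects will be screened for study eligibility within 28 days before the first injection of study treatment". If the reference were Day 1, a full 28 days after Screening, the 0–28 day row would fall to 0.2% with the day missing but would stay at 86% with the month missing. That choice therefore does not remove the problem, and an imputed date after the visit at which it was recorded is impossible whichever reference is used.

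Second, the impact is slight. A 300-day error in one record among 20 to 60 women per arm (an assumption) moves that arm's mean by 300/60 = 5 to 300/20 = 15 days, in a variable where every correctly recorded postmenopausal value exceeds 12 months. A negative minimum would also show in the planned table and listing. This stands, and it limits the point to a minor correction.

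**Conclusion.** The point holds in a limited form. The rule is wrong as written because it is uncapped. When the known month (day missing) or known year (month missing) is that of Screening, it places the last menstrual period after the visit at which it was recorded in almost every case, and the baseline summary can then include impossible negative times, such as −21 or −296 days in the example. The conditional percentages rest on evenly spread Screening dates; the broader shares also depend on assumed timing of the last period and an assumed mix of women. The actual frequency is unknown, and it is zero for women who are postmenopausal by the protocol definition. The variable is descriptive only: no eligibility rule, efficacy model or safety test uses it.

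**What to change.** Add one sentence to SAP 6.3.2.3: an imputed date later than the Screening Visit date is set to the Screening Visit date. Add one row to Table 16: time since last menstrual period equals the Screening Visit date minus the last-menstrual-period date. A capped record will show 0 days, which is still an imputed value but a possible one. The cost is one sentence, one table row and about one line of code.
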